#### **Treatment Plan: Expansion Cohort**

---

After the MTD/MFD of the combination therapy is defined, an expansion cohort of 8 patients will be treated to gain more experience regarding the tolerability of study treatment at the MTD/MFD and to assess the biological activity of the hCE1m6-NSCs using intracerebral microdialysis. Since it is anticipated that the MTD/MFD will be 150 million NSCs (dose level 4), the 6 patients who will be treated on dose level 4 will undergo intracerebral microdialysis and be counted as part of the expansion cohort.

Four patients in the expansion cohort will undergo intracerebral microdialysis after receiving NSCs at the time of surgery followed 2 days later by IV irinotecan, but the other 4 patients in this cohort will not receive NSCs on the day of surgery. Instead they will be given IV irinotecan 2 days after surgery, and dialysate samples will be collected from them to determine how much SN-38 is present in the brain from treatment with IV irinotecan alone. These 4 patients will then receive their first dose of NSCs through the Rickham on day 15 of cycle 1 followed by irinotecan on day 17.

To determine who will receive their initial NSCs administration on the day of surgery, and who will receive their first NSC administration on Day 15 via the Rickham catheter, participants will be stratified according to surgery type (craniotomy or biopsy), and, as each group enrolls participants, it will alternate between enrolling the participant to the Day 1 NSC start date and the Day 15 NSC start date. For example, the first craniotomy participant will be assigned Day 1 NSC start date, the second craniotomy participant will be assigned Day 15 NSC start date, the third will be assigned Day 1 NSC start date, the fourth will be assigned Day 15 NSC start date, and so on as applicable. The same alternate enrollment scheme will apply to participants undergoing the biopsy procedure. The rationale for this plan is to ensure to the degree possible an even distribution of start dates for each surgery group which should increase the ability for direct comparison. There is no requirement for specific number of biopsy or craniotomy participants in the expansion cohort.

If the DLT rate in the expansion cohort exceeds 34%, the toxicity data will be reviewed.

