**4. Injection of NSCs – A-J**

- Cells will arrive in the operating room already diluted into the final volume of 2% HSA/artificial CSF (per Table 8.2a). The cells are to remain at room temperature. Sterile technique will be used in the handling of cells. Refer to Table 8.2a for the number and volume of NSCs.
- For procedures A,C,E,G,I (MD catheter present), inject between two to four 100-150  $\mu$ L suspensions of NSCs at the margins of the catheter(s). The remaining number of NSCs will be injected in divided 100-150  $\mu$ L volumes as evenly spaced as possible throughout the wall of the resection cavity, administering them only into areas that are surgically safe and feasible.
- For procedures B,D,F,H,J (no MD catheter), inject the NSC volumes as evenly spaced as possible throughout the wall of the resection cavity, administering them only into areas that are surgically safe and feasible.
- The NSCs will be injected 2.5 cm deep and tracked up to approximately 1 cm deep, (slowly injecting as the needle is withdrawn, so as to distribute the NSCs from 2.5 cm – 1 cm depth).

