**4. Microdialysis Catheter – A, C, E, G, I, K**

- Before placing catheters into brain, flush with sterile artificial CSF
- For procedures A and C (no Rickham), a 70 Brain MD Catheter will be passively introduced into the injection site through the needle track. When feasible, a second microdialysis catheter will be inserted into a geographically different part of the tumor, as per the next bullet point.
- If a Rickham catheter or first MD catheter are in the biopsy site, tunnel an MD catheter subcutaneously, then insert into residual tumor or peritumoral tissue.
- Insert 1 to 2 MD catheters

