### Sample Size

---

The anticipated sample size is 29patients: minimum=6; maximum= 53(allowing for 42 patients for dose escalation through 5 possible dose levels of NSCs and 3 dose schedules of irinotecan, estimating ~3 patients to replace unevaluable/ineligible patients and an additional 8 patients for the expansion cohort).A sample size of 6 at the MTD/MFD will allow us to i) achieve a maximum margin of error for a 95% confidence interval for the DLT rate of 0.38 and ii) detect a 0.25 toxicity rate in approximately 82% of trials. The additional 8 patients in the expansion cohort, for a total of 14 patients treated at the MTD/MFD, will allow us to i) achieve a maximum margin of error for a 95% confidence interval for the DLT rate of 0.27 and ii) detect a 0.15toxicity rate in approximately 90% of trials.

An important purpose of the expansion cohort is to obtain information about the biologic activity of the hCE1m6-NSCs using intracerebral microdialysis. Sample size calculations based on preclinical results for the AUC from 0 to 20 hours (nMxhr) for SN38in rats (the combination therapy group mean= 7, sd=4.4; irinotecan alone mean=1.8, sd=1.2) implementing a natural log scale (mean difference 1.36 and sd=0.66) indicate 4 participants per group could provided 80% power todetermine if the addition of NSCs to treatment with irinotecan increases intracerebral concentrations of SN-38, using a one-sided two-sample t test with a 0.05 level of significance. As we expect our patient data to be more variable than the preclinical rat data we consider these results to be exploratory.

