#### 15.1.6 Analysis Plan:

---

Tables will be created to summarize all toxicities and side effects by dose, course, organ severity (by NCI CTCAE version 4.0), and attribution. Rates and associated 95% Clopper Pearson confidence limits will be estimated for DLTs and clinical benefit at the RP2D. Descriptive statistics will be provided for study patient demographics.

Pharmacokinetic data from patients who undergo intracerebral microdialysis will be summarized using descriptive statistics and graphical methods. The biologic activity of the hCE1m6-NSCs, based on comparison of microdialysis SN38 PK data from patients receiving NSCs + irinotecan vs patients receiving irinotecan alone, will be assessed using a one-sided two-sample t test. Regression analysis will be used to assess the relationship between hCE1m6-NSC dose and SN-38 concentrations in brain interstitium using microdialysis data from the patients treated with the initial NSC dose (n=6) and from the patients in the expansion cohort treated with the highest NSC dose (n=4). Other secondary objectives include assessing for possible development of NSC immunogenicity after first and repeat exposures, and—when feasible—evaluating the fate of the NSCs at autopsy. These results will be summarized using descriptive statistics and graphical methods.

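### The comparison of NSCs plus irinotecan with irinotecan alone assigns patients within surgery-type strata but is analysed without them; the plan should prespecify a surgery-type term

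*Combined protocol and SAP*

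**What the plan says.** **Assignment.** Section 5.4 (Treatment Plan: Expansion Cohort) states that "participants will be stratified according to surgery type (craniotomy or biopsy"). Within each group successive patients alternate between a Day 1 and a Day 15 NSC start. The reason given is to even out start dates within each surgery group so that the arms can be compared more directly. Section 5.2 repeats the scheme. Section 5.4 sets no number per surgery type.

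**Analysis.** The Analysis Plan in Section 15 says that the comparison of the NSC arm with "patients receiving irinotecan alone, will be assessed using a one-sided two-sample t test". The Statistical Considerations part of the Synopsis names the same test. Neither mentions surgery type, a stratified analysis or a sensitivity analysis.

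**Power.** Under Sample Size, "4 participants per group could provided 80% power" "using a one-sided two-sample t test with a 0.05 level of significance", "implementing a natural log scale (mean difference 1.36 and sd=0.66"). The same paragraph expects patients to vary more than the rats that supplied these values, and calls the results exploratory.

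**Procedures.** In craniotomy patients with a probe, part of the NSC dose is injected as "suspensions of NSCs at the margins of the catheter(s"). In biopsy patients with a Rickham the cells go through the Rickham, and the instruction for the probe is to "tunnel an MD catheter subcutaneously, then insert into residual tumor or peritumoral tissue". At dose level 4 a biopsy patient receives part of the Day 1 dose in surgery and the rest by infusion after recovery (Table 8.2b).

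**The concern.** The sponsor judged surgery type important enough to control at assignment and then left it out of the analysis. When arms are balanced within strata and the strata are ignored, any difference between strata that is common to both arms stays in the residual variance. The estimated effect is still unbiased, but its standard error is too large, so the test rejects too rarely and power falls. With 8 patients and 6 residual degrees of freedom there is little room for this.

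If the strata are not balanced between arms, a surgery difference can also bias the unadjusted comparison. That can happen here, because the numbers per surgery type are not fixed.

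The point concerns only the between-arm test, not the regression of SN-38 on NSC dose.

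**Working it through.** **1. Inputs (Sample Size).** Rat SN-38 AUC from 0 to 20 hours: "the combination therapy group mean= 7, sd=4.4; irinotecan alone mean=1.8, sd=1.2". On the log scale, ln(7/1.8) = 1.358, which agrees with the stated 1.36. SD 0.66, 4 per arm, one-sided 0.05.

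**2. The plan's figure.** Noncentrality = 1.36 / (0.66 × √(1/4 + 1/4)) = 2.914, with 6 df and critical value 1.943. Exact noncentral t power is 0.822. With 3 per arm it is 0.667, so 4 per arm is the smallest size that reaches 80%. The plan's figure reproduces.

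**3. With a surgery term, even splits.** For a model of arm plus surgery type, the variance factor v of the arm effect satisfies 1/v = Σ n₁n₀/(n₁+n₀), summed over strata.
- Split 4/4: 1 + 1 = 2.
- Split 6/2: 9/6 + 1/2 = 2.

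So v = 0.5 as before, and noncentrality stays at 2.914. The df fall to 5 (critical value 2.015) and power is 0.802, whatever the size of an additive surgery effect. The cost is 0.822 − 0.802 = 0.02.

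**4. Without the term, the same shift D in both arms, 4/4 split.** Each observation sits D/2 from its arm mean, which adds 8 × (D/2)² = 2D² to the residual sum of squares. The expected residual variance is 0.66² + 2D²/6. At 2-fold (D = ln 2 = 0.693) this is 0.436 + 0.160 = 0.596, an SD of 0.77 instead of 0.66. Simulated results, with every D an assumption:

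| Surgery difference, both arms | Power, unadjusted | Power, adjusted | Type I error, unadjusted |
|---|---|---|---|
| none | 0.82 | 0.80 | 0.050 |
| 1.4-fold | 0.80 | 0.80 | 0.045 |
| 2-fold | 0.73 | 0.80 | 0.031 |
| 2.7-fold | 0.64 | 0.80 | 0.018 |
| 4-fold | 0.48 | 0.80 | 0.007 |

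In a 6/2 split the unadjusted power is 0.76, 0.68 and 0.56 at 2-, 2.7- and 4-fold, against 0.80 adjusted. If all 8 patients have the same surgery, there is nothing to adjust and power is 0.82.

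**5. Surgery difference in the NSC arm only (average NSC effect held at 1.36, 4/4 split).**

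| Difference, NSC arm only | Unadjusted | Adjusted |
|---|---|---|
| 2-fold | 0.78 | 0.77 |
| 2.7-fold | 0.73 | 0.74 |
| 4-fold | 0.64 | 0.69 |

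An additive term removes only part of this pattern. If NSCs have no effect, surgery type has none either under this mechanism, so the unadjusted test keeps its 5% level.

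**6. Odd splits.** Section 5.4's example starts the craniotomy group with Day 1 and applies the same scheme to biopsy. Read as both strata starting with Day 1, a 5/3 or 7/1 split gives 5 patients against 3, not 4 against 4. At 7/1 the single patient of the smaller stratum is in the Day 1 arm, so a surgery shift D biases the unadjusted difference by D/5, which is 0.14 at 2-fold. If SN-38 is 2-fold higher in that stratum, the unadjusted type I error is about 0.07; the adjusted test holds 0.05.

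Power at these splits if surgery type has no effect:
- Unadjusted, 5 against 3: 0.80.
- Adjusted at 5/3: 1/v = 6/5 + 2/3 = 1.867, noncentrality 2.815, power 0.78.
- Adjusted at 7/1: 1/v = 12/7 = 1.714, noncentrality 2.698, power 0.75.

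**The case against.** The strongest objection is about mechanism. The documents' clearest difference between the surgery types is how NSCs reach the probe. Procedure K, the irinotecan-alone arm, receives no Day 1 NSCs, and the wording for placing its probe is essentially the same for craniotomy and biopsy. A difference that works through NSC delivery is therefore an interaction confined to one arm. Step 5 shows that adjustment then gains nothing at 2-fold and about 5 points at 4-fold, and the type I error is not distorted. This stands, and it limits the power argument. A shift in both arms remains possible, since a craniotomy removes tumor before the probe goes in, but the documents give no size for it.

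The second objection is that the plan has already qualified its power. It says 4 per group could give 80%, expects more variable patients, and calls the comparison exploratory; it is a secondary objective of a phase I trial. This also stands. Greater patient variability alone would lower power (0.68 at SD 0.80), and a surgery term recovers none of the part unrelated to surgery.

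The third is that one of 6 degrees of freedom is a real price at n = 8. That is so, but the price is about 2 points in even splits.

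None of this explains why the analysis departs from the assignment scheme, or protects the test when an odd split leaves surgery type unbalanced between arms.

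**Conclusion.** The mismatch is real and worth correcting. Three things support the change: the analysis should follow the stratified assignment, the test keeps its level if surgery type shifts SN-38 in both arms, and the comparison is protected when an odd split leaves the arms unbalanced.

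A reader might infer that the stated 80% power is simply lost. The documents do not support that. They give no craniotomy–biopsy difference in SN-38 and no surgery split. In a 4/4 split, adjustment gains power only above a difference of about 1.4-fold common to both arms. The losses to 0.73 and 0.64 need an assumed 2-fold or 2.7-fold shift in both arms. They nearly disappear as an argument for adjustment if the difference lies only in the NSC arm, and there is no loss if surgery type has no effect or only one type enrols. The excess type I error of about 7% needs a 7/1 split, both strata starting with Day 1, and 2-fold higher SN-38 in the single-patient stratum.

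The comparison remains exploratory either way.

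**What to change.** In the Analysis Plan and in the Synopsis, replace the unstratified test with a prespecified linear model of ln SN-38 AUC on arm plus surgery type, testing the arm term at one-sided 0.05. This also carries the log scale of the sample size calculation into the analysis. Omit the surgery term if only one surgery type enrols. Report arm means within each surgery type, which would show a difference confined to the NSC arm. Give the unadjusted t test as a sensitivity analysis. The choice should be fixed now, because choosing after seeing 8 patients' data would be data-driven.

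Cost: a sentence or two in each place and one degree of freedom. If surgery type has no effect, power falls from 0.82 to 0.80 in even splits, from 0.80 to 0.78 at 5/3 and from 0.80 to 0.75 at 7/1. No extra patients or samples are needed.

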#### Statistical Considerations:

Tables will be created to summarize all toxicities and side effects by dose, course, organ severity (by NCI CTCAE version4.0), and attribution. Rates and associated 95% Clopper Pearson confidence limits will be estimated for the DLTsand clinical benefit at the RP2D.Descriptive statistics will be provided for study patient demographics.

Pharmacokinetic data from patients who undergo intracerebral microdialysis will be summarized using descriptive statistics and graphical methods.The biologic activity of the hCE1m6-NSCs, based on comparison of microdialysis SN38 PK data from patients receiving NSCs + irinotecan vs patient s receiving irinotecan alone will be assessed using a one-sided two-sample t test.Regression analysis will be used to assess the relationship between hCE1m6-NSC dose and SN-38 concentrations in brain interstitium using microdialysis data from the patientstreated with the initial NSC dose (n=6) and from the patients in the expansion cohort treated with the highest NSC dose (n=4).Other secondary objectives include assessing for possible development of NSC immunogenicity after first and repeat exposuresand—when feasible—evaluating the fate of the NSCs at autopsy. These results will be summarized using descriptive statistics and graphical methods.

Sponsor:

City of Hope

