## Assigning Treatment and Correlative Study Regimen

---

A participant's starting NSC dose level, irinotecan dose schedule, correlative study procedures, and NSC regimen will be assigned by the Principal Investigator based on the following criteria:

1. Except where planned in the expansion cohort, participants who do not receive Day 1 NSCs will be replaced.
2. During the 3+3 stage of the trial, any participants who are not evaluable for dose escalation will be replaced.
3. During the 3+3 stage of the trial, the NSC dose level (-1,1,2,3, or 4) and irinotecan dose schedule (A, B, or C) will be determined using criteria defined in Section 5.3.
4. The first six patients enrolled to the trial will have microdialysis catheters inserted and undergo microdialysis and accompanying blood plasma PK studies. If one or more of the six patients does not receive cycle 1 day 3 irinotecan, the patient(s) will be replaced with the next patient(s) enrolled.
5. During the expansion cohort, all eight participants will have microdialysis catheters inserted and undergo microdialysis and accompanying blood plasma PK studies. N.B., since it is anticipated that the MTD/MFD will be 150 million NSCs (dose level 4), the 6 patients who will be treated on dose level 4 will undergo intracerebral microdialysis and be counted as part of the expansion cohort.
6. During the expansion cohort, all 8 participants will follow the NSC dose level and irinotecan dose schedule per the MTD (or if the MTD is not reached, the MFD), however 4 participants will receive their initial NSC administration on the day of surgery (Day 1), and 4 participants will receive their first NSC administration on Day 15. Participants will be grouped according to surgery type (craniotomy or biopsy). As each group enrolls participants, it will alternate between enrolling the participant to the Day 1 NSC start date and the Day 15 NSC start date. (See Section 5.4 for further explanation).

Based on the above criteria, the Principal Investigator will communicate to the clinical research team and the neurosurgeon the assigned biopsy or craniotomy procedure A-K as detailed in table 8.2a and table 8.2b.

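### The NSC dose versus SN-38 regression is in effect a 6-versus-4 comparison; an exploratory three-group model with the irinotecan-alone patients would also set the initial dose against background, and the group sizes need reconciling

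*Combined protocol and SAP*

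**What the plan says.** One secondary objective is to describe how NSC dose relates to SN-38 in brain interstitium. The Analysis Plan in Section 15 does this by regression on two microdialysis groups: "the patients treated with the initial NSC dose (n=6) and from the patients in the expansion cohort treated with the highest NSC dose (n=4". The synopsis (Statistical Considerations) repeats the restriction: "from the patients in the expansion cohort treated with the highest NSC dose (n=4". Neither place gives the model form, the outcome scale or the dose coding.

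The low-dose patients come from Section 5.2: "The first six patients enrolled to the trial will have microdialysis catheters inserted and undergo microdialysis". Dose levels 1 and 2 use the same NSC dose, 5×10^7. The highest dose is expected to be 1.5×10^8.

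Four expansion patients receive no NSCs on the day of surgery. Section 5.4 says of them that "dialysate samples will be collected from them to determine how much SN-38 is present in the brain from treatment with IV irinotecan alone". They serve a separate objective, biologic activity, which "will be assessed using a one-sided two-sample t test". The Sample Size section gives its basis: rat data on the log scale "indicate 4 participants per group could provided 80% power". It calls the results exploratory because patients should vary more than rats. All microdialysis data are also to be summarised descriptively and graphically.

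The documents disagree on the counts. The regression has 4 highest-dose patients. Sections 5.2 and 5.4 anticipate that "the 6 patients who will be treated on dose level 4 will undergo intracerebral microdialysis and be counted as part of the expansion cohort", a cohort of 8. The Sample Size section instead has "The additional 8 patients in the expansion cohort, for a total of 14 patients treated at the MTD/MFD".

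**The concern.** Two dose values give a line with nothing left over to test it. The fit can say whether SN-38 is higher at the highest dose than at the initial dose. It cannot say whether the relation bends, and its zero-dose value is an extrapolation, although zero-dose patients are dialysed in the same trial. No planned test or model says whether the initial dose raises SN-38 above what irinotecan alone produces.

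This matters most if the t test is positive and the slope is flat. The sponsor would then ask whether the initial dose already delivers the full effect, and the two planned analyses answer that poorly. At stake is the interpretation of a secondary, exploratory objective, not the dose recommendation.

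**Working it through.** **Inputs.** From the Sample Size section: ln difference 1.36, SD 0.66, one-sided 0.05, 4 per group. From the Analysis Plan: 6 initial-dose and 4 highest-dose patients. From Section 5.4: 4 irinotecan-alone patients. Assumed: highest dose 1.5×10^8, and larger SDs of 0.9 and 1.32 (the latter double the plan's value), since the plan expects more variability without giving a figure.

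**1. The plan's own figure.** ln(7/1.8) = 1.358, matching 1.36. The standard error is 0.66 × √(1/4 + 1/4) = 0.467 and the noncentrality 1.36/0.467 = 2.91. With 6 df, one-sided power is 82%; with 3 per group it is 67%. Four per group is confirmed.

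**2. The planned regression.** With doses 0.5 and 1.5 (×10^8), the slope is the difference in group means divided by the dose gap of 1.0, and its p-value is that of the pooled 6-versus-4 t test. Lack-of-fit df are 0.
- Highest versus initial, 95% half-width: t(0.975, 8) × 0.66 × √(1/6 + 1/4) = 2.306 × 0.426 = 0.982.
- Extrapolated zero-dose value: mean dose 0.9; sum of squares 6 × 0.4² + 4 × 0.6² = 2.4; half-width 2.306 × 0.66 × √(1/10 + 0.9²/2.4) = 1.007.

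**3. Three-group model, 4/6/4.** Residual df are 14 − 3 = 11 and t = 2.201. No linearity is assumed.
- Initial versus zero (new): 2.201 × 0.426 = 0.938, a factor of e^0.938 = 2.55.
- Highest versus initial: 0.982 falls to 0.938, about 5% narrower.
- Highest versus zero: 2.447 × 0.467 = 1.142 falls to 2.201 × 0.467 = 1.027, about 10% narrower.
- Background mean, now observed: 2.201 × 0.66/√4 = 0.726.

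**4. Power for initial versus zero** (two-sided 5%, 11 df). Under a full plateau the ln difference is 1.36. Under background plus an amount proportional to dose it is ln(1 + (e^1.36 − 1)/3) = 0.676.

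| SD | Plateau | Proportional |
|---|---|---|
| 0.66 | 83% | 31% |
| 0.9 | 57% | 19% |
| 1.32 | 31% | 11% |

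**5. Plateau or proportional?** Simulation of 40,000 trials per scenario gives the frequency of a positive t test with a non-significant slope, at SD 0.66 (0.9 in brackets): plateau 78% (57%), proportional 54% (44%), no NSC effect 4% (4%). The planned pair separates a plateau from no effect but hardly from proportionality. A lack-of-fit test of ln(b + k × dose) on the three groups rejects in 37% (21%) under the plateau and 5% (5%) under proportionality. At SD 1.32 its power is about 11%.

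**6. Group sizes.** Two illustrations at SD 0.66, both assumptions:
- All 6 dose level 4 patients receive day 1 NSCs and count within the 8, leaving 2 irinotecan-alone places. Half-widths are 0.84 (highest versus initial) and 1.19 (initial versus zero). For a 6-versus-2 t test the standard error is 0.66 × √(1/6 + 1/2) = 0.539, and power drops from 82% to 72%.
- The 8 are additional and the 6 are dialysed too, giving 10 highest-dose and 4 irinotecan-alone patients. Half-widths are 0.72 and 0.90.

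The safety figures move as well. The chance of seeing at least one event with a true rate of 0.15 is 1 − 0.85^14 = 90% for 14 patients, as the plan states, but 1 − 0.85^8 = 73% if the 6 are within the 8.

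**The case against.** The planned regression answers the dose question the protocol asks of the expansion cohort: does a higher NSC dose give more SN-38? NSC versus no NSC is a separate objective, and its t test has the better design, with concurrent, surgery-stratified alternating assignment. Initial dose versus background is not a named objective, and the descriptive summaries will show all three groups anyway. This largely stands. It makes the proposal an improvement, not the repair of an error.

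The added contrast is also the least secure. The low-dose patients enrol first and outside the alternation, so the comparison is non-concurrent. In craniotomy patients, Section 8.2 puts two to four injections of 100–150 µL at the catheter margins at every dose level, and Table 8.2a implies one cell concentration throughout. A plateau at the probe could therefore reflect fixed local delivery. Very low SN-38 is expected without NSCs, so logs and equal variance are most doubtful in that group. All of this stands and belongs in the text. The planned regression is non-concurrent too.

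A reader might infer that the trial lacks a background measurement. It does not: the irinotecan-alone patients are dialysed, tested and summarised. A reader might also infer that a three-group model would settle plateau versus proportionality. Its power of at most about 37% says otherwise.

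The split with 2 irinotecan-alone patients contradicts the explicit four-and-four allocation. It shows sensitivity only; it is not a reading of the plan.

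**Conclusion.** The concern holds in a limited form. The dose regression is a two-group comparison with no information on shape, and data already planned for collection are left out of the dose objective. Including them yields one useful new estimate, initial dose versus background to about 2.6-fold either way, and almost no gain for highest versus initial. This rests on rat-level variability, groups of 4/6/4, functioning catheters, a common irinotecan dose and distinct initial and highest doses. At twice the SD the half-width doubles to 1.88 ln units. Any comparison with dose-proportionality should be descriptive.

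The documents do not support saying that the planned regression is invalid, that the 4-per-group calculation is wrong, or that the RP2D is affected. The conflict over group sizes is real and needs resolving whether or not the model is added.

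**What to change.** Keep the planned fit and t test, and add to the Analysis Plan, with a matching line in the synopsis:

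> As an exploratory analysis, ln dialysate SN-38 AUC will be modelled in all microdialysis patients by the NSC dose actually received before microdialysis (zero, initial, highest; any other dose as its own group). Group means and pairwise ratios will be given with 95% confidence intervals. Equal variance will be checked, and unequal-variance intervals used if it is doubtful. The analysis will be restricted to one irinotecan schedule or adjusted for schedule. Rules for SN-38 below quantification and for combining two catheters in one patient will be set before the data are seen. Comparison with dose-proportionality (untransformed AUC as background plus an amount proportional to dose) will be descriptive. If the initial and highest doses coincide, only NSC versus no NSC will be reported. Low power, surgery type, the earlier non-alternating enrolment of the low-dose group and injection at the catheter margins will be stated as limitations.

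Separately, reconcile the numbers of highest-dose and irinotecan-alone microdialysis patients across Sections 5.2 and 5.4, the Sample Size section and the Analysis Plan, and restate the figures that depend on them.

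The cost is a paragraph, a synopsis line, two data-handling rules and the reconciliation. No new patients, samples or assays are needed. Restricting to one irinotecan schedule could reduce the numbers, and the change does not remove the early-versus-late enrolment difference.
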